The borough of St Helens has a legacy of poor health linked with deprivation and the town's industrial past. St Helens is ranked as the 26th most deprived local authority in England, its relative position having deteriorated since 2015 with almost 25% of residents living in the 10% most deprived neighbourhoods in the country (34). St Helens has widespread health deprivation with a higher-than-average diabetes prevalence of 9.2% (14,935 individuals) (20), versus 7.3% in England (35). Despite improvements in mortality rates over the last 20 years the borough's mortality rate remains higher than the national average as seen in figure 4 (36), with two thirds of adults recorded as overweight or obese, 1 in 5 adults are physically inactive and less than 50% eat the recommended '5 a day' (37).

Source: NHS Digital. Primary Care Mortality Database (PCMD) *2018 & 2019 St Helens figures are provisional

Figure 4: All-age all-cause mortality trend 1999-2019 (36)

RATIONALE FOR CURRENT STUDY

Despite the current literature evidencing the clear benefits of DSME on behavioural choices, HbA_{1c} levels and reduced risk of morbidity and premature mortality (38) attendance and completion levels remain poor. There is minimal understanding of the impact of non-completion of DSME programmes on HbA_{1c} or psychometric outcomes. Positive endpoints for DSME studies are typically based on participants who complete the full programme (22) with HbA_{1c} (39) used as a measure of effectiveness yet often studies fail to demonstrate significant or lasting results despite being statistically powered (38).

There is scarce literature examining the impact of attrition on DSME effectiveness. Although a small retrospective study in the USA using secondary data analysis of 105 patient records reported patients who attended 1 or 8 hours or more of DSME had a significant reduction in HbA_{1c} when compared to those who received no education (22). Evidence is available looking at diabetes prevention programmes which suggests each session attended is linked to a reduction in body weight between 0.26-0.3% (24,40) suggesting a positive impact with any level of engagement.

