Internationally the benchmark for recording a patient as completed DSME is attendance at $\geq 60\%$ of a programme's content (23,41–43), a discord with the literature measuring effectiveness of landmark studies at 100% completion (25,39). A record of DSME attendance is given for patients who sign up and engage with $>10\%$ of materials (23,41,43).

There is no research available measuring the impact of non-completion on UK DSME programme effectiveness or internationally on the impact of differing completion rates on patient reported outcome measures (PROMs) despite the acceptance of completion ($\geq 60\%$) at discord with legendary studies benchmarking completed at 100%. The aims of this study are to explore if patients who attend minimal aspects (10%) of DSME programmes gain clinically significant improvements in ability to self-care compared to those who do not attend, and if the nationally accepted 60 % completion rate is as effective as 100% completion.

THEORETICAL FRAMEWORK

Philosophical assumptions (also referred to as epistemology) influence our views about how phenomena should be approached (44) assisting researchers in refining the types of evidence required, how it should be collected, and how it should be interpreted. This quantitative study will adopt an experimental hypothesis driven design whereby the variable or intervention is controlled, with the exception of a control group, to attempt to establish causal effect of an intervention, in this case DSME completion rates. Whilst the most powerful and highly regarded form of experimental study remains the randomised control trial (RCT), this study will test the feasibility of conducting a full RCT.

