4.1 Null hypothesis

Differing DSME completion rates have no impact on a person's ability to self-care, diabetes distress or health related quality of life.

RESEARCH QUESTION

Using a quantitative approach this feasibility study aims to explore if patients who attend minimal aspects (10%) of DSME programmes gain clinically significant improvements in ability to self-care compared to those who do not attend, and if the nationally accepted 60 % completion rate is as effective as 100% completion on patient reported outcome measures.

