6.2 Study processes

Screening and recruitment

Potentially eligible participants meeting the inclusion criteria and not excluded by exclusion criteria (outlined in section 8.1) who are either due to attend the diabetes centre for new patient clinic, have been referred for DSME intervention or are on the monthly shared care report for newly diagnosed type 2 diabetes requiring an offer of DSME will be screened for entry into the study and added to a screening log sheet (appendix 1). Potentially eligible participants due to attend new patient clinic will be invited into the study by NP clinic letter (appendix 1) with attached participant information sheet (PIS) (appendix 1). Letters will be posted ahead of their clinical appointment. For potential eligible participants identified through DSME referrals or the monthly shared care record report will be sent a telephone screening letter (Appendix 1) and PIS prior to meeting with the researcher. Study recruitment technique is outlined in further detail in section 8.2.2.

At the screening meeting potentially eligible participants will be asked to confirm they have read the PIS and invited to ask questions about the research. Where patients decline to take part in the research, they will be reassured this will not have any impact on their current or future treatment. Participants who give written informed consent will be enrolled onto the study. The researcher will utilise an informed consent checklist (Appendix 1) to ensure consistency and that all elements for informed consent have been completed. Participants will be consented for informing their GP, this is made clear in the PIS.

Visit 1

At enrolment baseline characteristics will be recorded from the electronic medical record, or where not available directly from the patient: NHS number, age, sex, ethnicity, diabetes duration, postcode, latest HbA_{1c}, prescribed glucose lowering agents, and a Charlson Comorbidity Index will be calculated. Postcode will be used to calculate indices of multiple deprivation (IMD) score.

Participants (n=120) will be randomised by permuted block strategy of 2:1 across four groups using an online randomisation software application designed for clinical trials (51,52). Due to the design of this study randomisation will not be blind to the researcher or participants. Group design will be as follows:

- Group 1: DSME 6 hours, 100% completed (completed).
- Group 2: DSME 3 hours 36 minutes, 60% completion (partial completion)

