- Group 3: DSME 36 minutes, 10% of content (attended)
- Group 4: Delayed education (education not offered, not attended, or declined)

DSME programme overview is provided in appendix 1 giving a broad overview of DSME content by programme completion status. Local demographic data suggests that of the local population 46.4% are living in the most deprived neighbourhoods within the UK (9). Of the local population 19.3% have a reading age of 9-11 or below (53,54), are classed as being functionally illiterate and are therefore likely to struggle reading a paper questionnaire. Verbal support for completing the PROMs will be offered by the researcher to ensure participants from lower socioeconomic backgrounds are not excluded from participating in the DIABETES PRO study as they are evidenced to make up a larger proportion of people with diabetes (55-57). Support will be limited to reading the questions verbatim.

Participants will be asked to complete three psychometric tests measuring self-care activities, diabetes distress and quality of life using the following validated tools: Diabetes Self-Management Questionnaire-Revised (DSMQ-R)(48), Problem Areas in Diabetes (PAID) scale (49) and the Patient Reported Outcome Measures Information System (PROMIS) Global Health scale v1.2 (50) (appendix 1).

Participants in groups 1, 2 and 3 will be asked to book a DSME session with the researcher, typically this should be no longer than 3 weeks from study enrolment. Research group DSME programmes (intervention) will be run by the researcher separate to routine patient DSME to minimise disruption of participants leaving part way through on patients.

Participants randomised to group 4, delayed education will not be required to attend DSME as part of the DIABETES PRO study. Collected data will be collected and managed using Research Electronic Data Capture (REDCap) electronic data capture tools. A REDCap data collection tool has been included in Appendix 1 for reference. REDCap is a secure, web-based software platform designed to support data capture for research studies, providing an intuitive interface for validated data capture; audit trails for tracking data manipulation and export procedures; automated export procedures for seamless data downloads to common statistical packages; and procedures for data integration and interoperability with external sources (58,59) (see section 3.6 for further details).

Visit 2

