6.4 Data Analysis

Descriptive analysis will be completed for all demographic data presenting continuous variables as means \pm standard deviation and categorical variables as numbers (%). Data will be tested for normality using a Shapiro-Wilk test and subject to visual inspection of histograms and normal Q-Q plots.

Psychometric outcomes will include the Diabetes Self-Management Questionnaire-Revised (DSMQ-R)(48), Problem Areas in Diabetes (PAID) scale (49) and the Patient reported outcome measures information system (PROMIS) Global Health scale v1.2 (50). Data will be treated as continuous and analysis of the difference in the mean before and after intervention will be conducted using an analysis of variance (ANOVA) test to check for statistical and clinical difference in the mean across the four groups.

Statistical analysis will be conducted using IBM® SPSS® Premium 29 with support from University of Liverpool statisticians. The alpha level will be set at 5% for statistical significance.

Whilst a statistically significant difference is desirable, it is important to understand what would represent a meaningful clinical change for a patient. As such the minimal clinically important difference (MCID) will be reported to measure the smallest difference in which the patient would perceive a benefit (61–64). Where the MCID is not published this will be calculated using a distribution-based derivation using 0.5 SD of the observed change in PROM score (62,65). Whilst this approach is not without its limitations (61,63) no consensus on the ideal means of determining the MCID is available (63). A systematic review concluded that 0.5 SD of the observed change approximated the published MCID in the majority of cases popularising this derivation in the literature (65).

MCID will be classed as >2 T-score points for the PROMIS Global Health v1.2 (66) in which physical health and mental health are given separate T-scores with a 95% confidence interval. The MCID will be calculated for PAID and DSMQ-R.

Recruitment of participants and the number of dropouts will be reported descriptively (frequencies and percentages). Due to the aims of this study considering differing completion levels of DSME, intention to treat analysis will not be used. Where participants allocated to a group do not fully complete the required amount of DSME there results would be withdrawn from the final analysis.

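### The aims ask whether 60% completion is as effective as 100% but name no comparison of either with delayed education, so similar results could be read as equal effectiveness when neither worked

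*Combined protocol and SAP*

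**What the plan says.** The aims appear in the Study Summary, in Rationale for Current Study and under Research Question. They name two comparisons:

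- Whether people who receive 10% of the programme "gain clinically significant improvements in ability to self-care compared to those who do not attend". This is Group 3 against Group 4.
- Whether 60% matches 100%: "if the nationally accepted 60 % completion rate is as effective as 100% completion" in the Rationale, repeated under Research Question as "if the nationally accepted 60 % completion rate is as effective as 100% completion on patient reported outcome measures". This is Group 2 against Group 1.

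Neither aim sets the full programme, or 60% of it, against delayed education.

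Other parts of the plan are broader. The null hypothesis in Section 4.1 is global: "Differing DSME completion rates have no impact on a person's ability to self-care, diabetes distress or health related quality of life". The research question in Section 5.1 covers differing completion rates without restriction. Section 6.2 randomises a concurrent delayed-education group.

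Section 6.4 analyses pre-to-post change by ANOVA "to check for statistical and clinical difference in the mean across the four groups", at a 5% alpha. It names no contrast, post hoc procedure, margin or decision rule for any pair of groups. Section 6.1 declares the study not statistically powered.

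**The concern.** A statement that 60% is as effective as 100% means something only if 100% has an effect in this trial. Group 2 v Group 1 cannot show that. A non-inferiority margin for that pair would not show it either, because two inert programmes also lie within a margin of each other.

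The effect of the full programme should be estimated here, not assumed. The Rationale says that "often studies fail to demonstrate significant or lasting results despite being statistically powered". That remark concerns HbA1c, and Section 6.1 cites questionnaire gains at 4 months, but from other studies. Neither settles what this programme does to the DSMQ-R in this population.

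The 60% figure is the national completion benchmark, so a finding that 60% is enough would attract attention. If the true position is that no effect was seen at any level, that finding would mislead. The size of full education v none is also an obvious quantity for planning the full RCT, yet it is not a named estimate.

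**Working it through.** **Inputs from the plan.** Four groups of 30, 120 in total, within a range of 24 to 50 per group (Section 8.2.1). Alpha 5% (Section 6.4). Green retention criterion above 80% (Table 3).

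**The plan's own figure.** 4 × 30 = 120. If 24 per group are wanted for analysis and 20% are lost (an assumption taken from the retention criterion), 24 / (1 − 0.20) = 30. The total reproduces. There is no power calculation to reproduce.

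**Assumptions.** The plan gives no effect size or SD, so effects are in units of the SD of change. Benefits of 0.5 and 0.8 SD are illustrative. Tests are two-sided at 5%.

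**Precision and power of one pairwise contrast.** With the variance pooled over four groups, half-width = t(0.975; 4n − 4) × √(2/n). Power uses the two-sample t test with non-centrality d × √(n/2).

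| Analysed per group | Half-width of 95% CI | Power, 0.5 SD | Power, 0.8 SD |
|---|---|---|---|
| 30 | 1.981 × 0.258 = 0.51 SD | 48% | 86% |
| 24 | 1.986 × 0.289 = 0.57 SD | 40% | 77% |

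**Can Group 2 v Group 1 alone tell the cases apart?** Four normal groups were simulated with SD 1 and a pooled variance. Means are for Groups 1, 2, 3 and 4.

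| True means (SD) | n | 2 v 1 non-significant | ANOVA significant | ANOVA significant and 2 v 1 non-significant | 1 v 4 favours DSME and 2 v 1 non-significant |
|---|---|---|---|---|---|
| 0, 0, 0, 0 | 30 | 95% | 5% | 3.1% | 2% |
| 0.5, 0.5, 0, 0 | 30 | 95% | 61% | 56% | 46% |
| 0.8, 0.8, 0, 0 | 30 | 95% | 96% | 92% | 83% |
| 0.5, 0.5, 0, 0 | 24 | 95% | 50% | 46% | 38% |
| 0.8, 0.8, 0, 0 | 24 | 95% | 91% | 86% | 75% |

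The 2 v 1 column is the same whether both levels work or neither does, so that comparison carries no information on the point.

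**Would a margin alone help?** With an assumed margin of 0.5 SD, Group 2 would be declared non-inferior to Group 1 in 40% (n = 24) to 48% (n = 30) of trials in which neither level works. Also requiring Group 1 to beat Group 4 cuts this to about 0.1 to 0.3%.

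**What the ANOVA leaves open.** A significant F does not say which groups differ. A non-significant F fits both readings. With a shared 0.5 SD benefit, F is non-significant in 100 − 61 = 39% of trials at 30 per group and 100 − 50 = 50% at 24.

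**Is non-significance an adequate meaning of similar?** No. At 30 per group with true means 0.8, 0.4, 0, 0, so that 60% yields half the benefit, Group 1 beats Group 4 while 2 v 1 is non-significant in about 54% of trials. With 0.5, 0, 0, 0, so that 60% yields nothing, this happens in about 16%.

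**The case against.** The strongest reply is that delayed education is a concurrent randomised control and is already in the planned test. The global null and Section 5.1 cover every level. If nothing works, the ANOVA fails to reject in 95% of trials, and the natural report is that no impact was shown. Reading a non-significant 2 v 1 result only after a significant F would leave the misleading pattern in 3.1% of null trials, against 2% with an explicit Group 1 v Group 4 requirement. The added protection over that reading is about one percentage point.

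Most of this stands, and it rules out three stronger readings that a reader might infer:

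- That the trial has no comparison of full education with none. The groups are randomised and the data will exist; what is missing is a named contrast.
- That two ineffective levels would be reported as equally effective. No section contains such a rule, so could is the most the text supports.
- That the trial aims to demonstrate equal effectiveness. The text says explore.

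Two things remain. The plan does not say that the 60% v 100% aim will be read only after a significant F. And the reply does not help when F is non-significant, a common outcome at this size even if the programme works.

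It is also fair to object to a pure significance gate in a study declared not powered. As shown above, such a gate would still let non-significance pass for similarity.

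**Conclusion.** The concern holds as a gap in the named comparisons. The aims ask whether 60% is as effective as 100%, neither level is set against delayed education, and an omnibus ANOVA without contrasts cannot supply the missing link. Similarity of Groups 1 and 2 could therefore be read as equal effectiveness when neither differs from no education.

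The size depends on how the results are read. Judged on 2 v 1 alone, the two cases cannot be distinguished (95% non-significant in each). Read only after a significant F, the misleading pattern is rare (3.1%), but the question stays unresolved in 39 to 50% of trials under a shared 0.5 SD benefit. These figures assume normal data, a common SD and 24 to 30 analysed per group. The effect sizes and the 0.5 SD margin are assumptions.

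This should be changed before results are seen. It does not undermine the design, and it is one instance of a wider omission, since Section 6.4 names no contrast for either stated aim.

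**What to change.** In Sections 5 and 6.4, pre-specify these differences in DSMQ-R change, each as an estimate with a 95% confidence interval from the same four-group model:

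- Group 1 v Group 4
- Group 2 v Group 4
- Group 2 v Group 1
- Group 3 v Group 4 (the existing aim)

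Add two sentences on wording:

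- A non-significant Group 2 v Group 1 difference will not be described as showing that 60% is as effective as 100%.
- The Group 2 v Group 1 interval will be interpreted only alongside the Group 1 v Group 4 interval. If the latter includes zero, the report will say that an effect of full DSME was not shown and that the 60% v 100% comparison is uninformative about effectiveness.

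The cost is protocol text and a few contrasts from data already planned; no arm, visit or participant is added. The downside is that firm claims will be rare. Group 1 v Group 4 would exclude zero in only about 40 to 48% of trials for a 0.5 SD effect and 77 to 86% for 0.8 SD. About 63 analysed per group would be needed for 80% power at 0.5 SD.

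One caution: Section 6.4 removes participants who do not complete their allocated amount. Group 4 has no session to complete, so the comparisons with Group 4 inherit that imbalance, and the report should say so.

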6.1 Design

This is a single-centre randomised feasibility study evaluating the impact of different completion rates of DSME programmes on psychometric outcomes specifically looking at ability to self-care, diabetes distress and quality of life. DSME will be the intervention and will typically be delivered within 3 weeks of the baseline appointment. There is a deliberate short separation between education intervention and follow up psychometric tests of 3-4 months to allow participants the opportunity to adopt any behaviour changes following the DSME programme whilst minimising the risk of not receiving the full NICE recommended DSME programme and to broadly align with landmark studies. Landmark studies namely DCCT (26,27) and DESMOND (25) evidenced a statistically

significant improvement to PROMs at 4 months post education intervention, however HbA_{1c} changes were not significant within this timeframe despite being statistically powered. A recent systematic review (38) concluded that as DSME is primarily focused on behavioural change to facilitate glycaemic control, efficacy measures should focus on behavioural and psychosocial changes, however these are often overlooked. This study is a feasibility trial and by its very nature is not statistically powered, therefore despite HbA_{1c} being arguably the measure of choice within the literature for measuring effectiveness of diabetes interventions, this study will use PROMs as its primary outcome measure.

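### The plan asks whether 60% completion is as effective as 100%, but it sets no margin and tests only for a difference, so a non-significant result cannot answer the question

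*Combined protocol and SAP*

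**What the plan says.** The 60% versus 100% question appears in three places in the protocol: the aims in the Study Summary, the end of the Rationale ("if the nationally accepted 60 % completion rate is as effective as 100% completion") and section 5, Research Question ("if the nationally accepted 60 % completion rate is as effective as 100% completion on patient reported outcome measures"). The verb is exploratory: "this feasibility study aims to explore if patients who attend minimal aspects (10%) of DSME programmes gain clinically significant improvements", with the 60% clause following in the same sentence.

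The null hypothesis in section 4.1 is one of no difference: "Differing DSME completion rates have no impact on a person's ability to self-care", and likewise for diabetes distress and quality of life.

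Section 6.4 specifies an ANOVA on the before–after change "to check for statistical and clinical difference in the mean across the four groups", and adds: "The alpha level will be set at 5% for statistical significance". It does not say whether that is one- or two-sided. It also gives MCIDs: more than 2 T-score points for PROMIS Global Health and, where none is published, half an SD of the observed change. It says the MCID will be calculated for DSMQ-R and PAID. No MCID is linked to the 60% versus 100% comparison, and no confidence interval for that comparison is specified.

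On size, section 6.1 states: "This study is a feasibility trial and by its very nature is not statistically powered". Section 8.2.1 takes 30 per group from a 24–50 per group feasibility range. Section 6.4 removes participants who do not complete their allocated amount, so the analysed groups may be smaller than 30.

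**The concern.** To call 60% completion as effective as 100%, one must say how much worse 60% could be and still count as equal. The plan never says. With a null of no impact and a 5% difference test, the favourable answer for 60% coincides with the null itself. A difference test cannot establish its own null: failing to reject becomes more likely as the groups shrink or the scores get noisier, whatever the truth.

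The MCIDs do not close the gap. They are described as the smallest change a patient would notice as a benefit, not as an acceptable loss. For DSMQ-R and PAID the half-SD value comes from the trial's own data, so it is unknown until the results are in.

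At stake is the message about the national 60% completion benchmark that the study sets out to examine. A non-significant result could be taken as support for that benchmark when the data are equally compatible with a meaningful loss.

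**Working it through.** **The plan's own figure.** 4 × 30 = 120. No effect size, SD, power or margin is given, so there is no power calculation to reproduce.

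**Inputs.**
- n = 30 per group (section 8.2.1).
- n = 24 per group: the lower end of the plan's range, and 80% of 30, which is the edge of the green retention band in Table 3.
- Alpha 5% (section 6.4), taken as two-sided. One-sided 5% is shown as the alternative.
- No SD is given, so results are in SD units of the change score. The 0.5 SD loss is an illustrative size borrowed from the half-SD rule in 6.4.
- Assumptions: normal change scores, equal SDs, independent participants, equal groups. Section 6.2 also mentions a 2:1 allocation, which does not match 30 in each group; 30 each is used here.

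**Step 1. 60% truly loses 0.5 SD: how often is the result non-significant?**

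*Direct Group 2 v Group 1 t-test* (not specified in the plan). Noncentrality = 0.5 × √(n/2), df = 2n − 2.

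| n per group | Noncentrality | Critical t | Non-significant |
|---|---|---|---|
| 30 | 0.5 × √15 = 1.936 | 2.002 | 52% |
| 24 | 0.5 × √12 = 1.732 | 2.013 | 60% |

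*Planned four-group ANOVA.* Noncentrality λ = n × Σ(mean − grand mean)², df = 3 and 4n − 4. Means are in SD units for Groups 1 to 4.

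| Means | Σ | λ at 30 / 24 | Non-significant at 30 / 24 |
|---|---|---|---|
| 0.5, 0, 0, 0 | 0.375² + 3 × 0.125² = 0.1875 | 5.625 / 4.5 | 52% / 62% |
| 0.25, −0.25, 0, 0 | 2 × 0.25² = 0.125 | 3.75 / 3.0 | 67% / 74% |

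The first pattern has only the full programme working. The second is the arrangement of a 0.5 SD gap between Groups 1 and 2 that the ANOVA finds hardest to detect. It is not dose-ordered, so it serves as a limiting case.

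**Step 2. 60% and 100% truly identical: how often would a confidence interval exclude a 0.5 SD loss?**

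95% CI half-width = t × √(2/n): 2.002 × √(2/30) = 0.52 SD; 2.013 × √(2/24) = 0.58 SD. At 30 per group the 60% arm must therefore come out about 0.02 SD *better* than the 100% arm before a 0.5 SD loss is excluded.

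| Rule | n = 30 | n = 24 |
|---|---|---|
| 95% CI (one-sided 2.5%) | 48% | 40% |
| 90% CI (one-sided 5%) | 61% | 52% |

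**Step 3. What margin would be met reliably?** For an 80% chance of passing with identical arms, using a 95% CI, the margin must be about 0.74 SD at 30 per group or 0.83 SD at 24. Conversely, a 0.5 SD margin needs about 2 × (1.96 + 0.8416)² / 0.5² = 62.8, so 63 per group.

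**Step 4. PROMIS.** Taking the plan's 2-point threshold as if it were a margin, with assumed change-score SDs of 4, 5, 7 and 10 T-points, the chance of passing at 30 per group is about 49%, 34%, 20% and 12% (normal approximation, 95% CI, identical arms).

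**The case against.** The strongest defence is that this is a declared feasibility study. The aim is to explore, the Abstract calls the outcomes preliminary, section 6.1 says the study is not powered, and section 8.2.1 sizes the groups to estimate effect sizes. Low power is therefore disclosed and is not a defect. That stands. It does not excuse the pairing of question and test: an unpowered study is exactly where non-significance should not be read as equal effectiveness.

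A second defence is that 6.4 looks at clinical as well as statistical difference, so significance is not the only yardstick. That also stands. But the clinical yardstick is not attached to this comparison or described as a tolerable loss.

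Two stronger readings are tempting, and the documents support neither:

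- A reader might infer that no defensible margin could be met, so the study can never reach the conclusion. The figures say otherwise: a 0.5 SD margin would be met about half the time at 30 per group if the arms are identical. Which margin is defensible is a judgement the protocol does not settle, since it gives no expected benefit of the full programme.
- A reader might infer that the plan intends to report non-significance as equality. No passage says so. The gap is that nothing rules it out.

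**Conclusion.** The point holds as a mismatch between aim and analysis. The plan poses an 'as effective as' question, gives no non-inferiority or equivalence margin, and specifies only a difference test, so a non-significant result cannot support that conclusion. A true 0.5 SD loss would go undetected by the planned ANOVA in roughly half to two-thirds of trials at 30 per group, and more often at 24. Even with a margin added, one of 0.5 SD or less could not be met reliably at these sizes.

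The percentages rest on normality, equal SDs, equal groups and an illustrative 0.5 SD effect. Baseline adjustment could improve precision but is not planned. The absence of a margin, and the fact that the test addresses a different question, depend on none of these assumptions.

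**What to change.** 1. In the Study Summary, the Rationale and section 5, replace the clause asking whether 60% is as effective as 100% with:

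> *to estimate the difference between 60% and 100% completion in change in DSMQ-R (primary), PAID and PROMIS Global Health scores, each with a 95% confidence interval, to inform the non-inferiority margin and sample size of a full RCT.*

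In section 5, also delete the trailing words about patient reported outcome measures, which the new clause already covers.

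2. Add to section 6.4:

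> *The Group 1 minus Group 2 difference will be reported with its 95% confidence interval for each measure. A non-significant result will not be reported as showing that 60% completion is as effective as 100%, and no conclusion of non-inferiority or equivalence will be drawn from this study.*

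The cost is a protocol wording amendment, with no extra participants, visits or data. The downside is a more modest stated aim. It fits the purpose the protocol already gives: testing the feasibility of a full trial and estimating effect sizes for it.
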